10.13 Number of Oxygen Free Days

Subjects will be considered oxygen free on a trial day if they do not have supplemental oxygen usage on that day. Supplemental oxygen usage is defined in Section 10.10 and subjects will be assessed for supplemental oxygen usage on each post treatment day up to trial Day 29 (i.e. from trial Day 2 to Day 29).

The number of oxygen free days for a subject will be the sum of the number of oxygen free days in hospital and number of oxygen free days at home if applicable. These days do not need to be consecutive. Missing data will be imputed as per Section 10.19.1.

10.14 Number of Respiratory Failure Free Days

The number of days a subject is free of respiratory failure will be the number of days a subject has a score of ≤ 5 on the ordinal scale post-baseline.

If a subject dies, they will be considered in respiratory failure from the date of death up to Day 60.

For hospitalized subjects this will be the number of days a subject has a score of ≤ 5 on the 8-point ordinal scale CRF page. Up to Day 29, the adjusted 8-point ordinal scale will be used, for days between Day 29 and Day 60 the following rules will apply:

- If the clinical status on both days is ≥ 6 the subject will be assumed to be in respiratory failure for all days between Day 29 and Day 60.
- If the clinical status on both days is ≤ 5 and there is no observed data (for example unscheduled visits) indicating a worsening of status the subject will be assumed to be respiratory failure free for all days between Day 29 and Day 60. If there is a worsening of a status such that the ordinal scale has a value of ≥ 6 , the subject will not be considered respiratory failure free from the duration of this status (if duration of status is known).
- If the clinical status at Day 29 is ≥ 6 and Day 60 is ≤ 5 and the date of the change of status is known, the subject will be counted as respiratory failure free from the date the status improved. If the date of change in status is unknown (for example data is imputed), only Day 60 will be counted as respiratory failure free.
- If the clinical status at Day 29 is ≤ 5 and Day 60 is ≥ 6 and the date of the change of status is known, the subject will be counted as respiratory failure free until the date the status worsen. If the date of change in status is unknown (for example data is imputed), only Day 60 will be counted as in respiratory failure.

For discharge subjects, if a subject does not have a change in status up to Day 60 following discharge i.e. they are not re-hospitalized due to a COVID-19 related illness, the number of respiratory failure free days after discharge will be calculated as

$$\text{Respiratory Failure free (days)} = \text{Day 60 visit} - \text{Date of Discharge} + 1$$

If a subject is re-hospitalized due to a COVID-19 related illness and the ordinal scale on re-admission is ≥ 6 the number of respiratory failure free days after discharge and prior to re-hospitalized will be calculated as

$$\text{Respiratory Failure free (days)} = \text{Date of re-hospitalization} - \text{Date of Discharge}$$

The number of respiratory failure free days will be the sum of the days the subjects met the criteria i.e. the number of days a subject has a score of ≤ 5 on the 8-point ordinal scale while hospitalized and the numbers of days a subject meets the criteria while discharged. These days do not need to be consecutive.

Subjects with missing data will have their data multiply imputed as per Section 10.19.1.

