10.9 Visit Windowing

Subjects are expected to attend daily visits until hospital discharge. Visits will be re-initiated in case of a COVID-19 related hospital re-admission. Subjects who do not discharge will have daily assessments up to Day 29. Subjects who do discharge will have visits Day 8, 15, 22, 29, 60. All subjects will have a follow-up visit at Day 60.

No visit windowing will occur for the 8-point ordinal scale. Daily values for the 8-point ordinal scale will be assigned based on the trial day the assessment occurs i.e. the value recorded on trial day X will be assigned as the value of the ordinal scale at Day X in the analysis. For discharged subjects, information on the oxygen use at home between visits will be entered on the concomitant medication page and the daily 8-point ordinal scale value for discharged subjects will be derived. If a subject has oxygen use on a trial day as per Section 10.10, they will be assigned a value of 2 on the adjusted 8-point ordinal scale (refer to Table 3 in Section 10.8) on the trial days between the oxygen start and end day. If Day 29 occurs on trial day greater than 29, for the analysis purposes a value of Day 29 will be assigned. For Day 60 the value collected at the Day 60 visit will be used in the analysis, even if this did not occur on trial Day 60. All endpoints for the 8-point ordinal scale will summarize Day 8, 15, 22, 29 and were applicable Day 60 time points. If a subject has multiple non-missing ordinal scale assessments on a trial day the assessment that occurred on the scheduled visit per the eCRF will be used in the analysis.

For hospitalized subjects, vital signs, supplemental oxygen use and oxygen saturation will be collected daily. Therefore, no visit windows will be assigned and results in the analysis will be summarized for each trial day up to Day 29. Trial day calculation is defined in Section 10.2. If the trial day an assessment occurs on does not align with the visit trial day in the CRF, the trial day will take precedence in terms of analysis. Laboratory assessments (including CRP and LDH) will be conducted while in hospital but not daily. Analysis visit windows as defined in Table 4 will be used for laboratory assessments. If a subject has multiple assessments in a window, the visit closest to the target day will be selected. For visits that are equally close to the target day, the assessment latest in time will be selected.

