10.19.1 Multiple Imputation

Missing ordinal scale data at scheduled time points will be imputed using multiple imputation. Multiple imputation relies on the assumption of data being missing at random (MAR) i.e. the missingness can be explained by the observed data and missing data does not depend on unobserved data after accounting for observed factors. Subjects will only have missing data imputed for post-baseline scheduled visits (Day 2 to Day 29, Day 60).

The following steps will be used to impute the missing data. Prior to the missing data imputation all observed 8-point ordinal scale data will be re-mapped per Table 3 to ensure discharged subjects with supplemental oxygen use are treated as clinically worse than discharged subjects with no oxygen use. This will also ensure information on at home oxygen use is explicitly contained in the ordinal scale score. The value of the adjusted 8-point ordinal scale to use in the analysis for all days following discharge will be assigned as per Section 10.10. On the day of discharge, the following rules will be used to assign a value of the adjusted ordinal scale:

- If a subject has a scheduled visit with an ordinal scale value other than 2, this value will be used in the analysis for the day of discharge.
- If a subject has a missing assessment or a value of 2 is recorded as the scheduled assessment, a subject will be assigned a value of 1 or 2 on the adjusted 8-point ordinal scale on the day of discharge as outlined in Section 10.10.

If a subject has an ordinal scale value of 8 at any visit or the subject has a date of death, records on or following date of death will be handled as follows in the analysis:

- All days following day of death will be set to 8.
- For the day of death, if the subject has a non-missing value on the ordinal scale that is not a value of 8 this will be the value used in the analysis.
- If a subject has a missing value on the day of death the value of 8 will be used.

Subjects who die will be removed from the Imputation in step 2. Only subjects who have not died will have their data imputed. Following the imputation, data for subjects who died will be included in all imputed datasets as observed.

A random seed of 2188 will be used for all imputation in this analysis.

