12.5.3.2 Time to Sustained Hospital Discharge

Time to sustained hospital discharge, will be defined as time to discharge after which no re-hospitalizations due to COVID-19 occur. Please refer to Section 10.12 for further details on this calculation.

Treatment groups will be compared using a stratified log-rank test adjusting for treatment, actual baseline disease severity and region. The size of the treatment effect will be estimated as a hazard ratio, obtained using a Cox proportional hazards regression model and the Cox regression model will include a factor for

randomized treatment, baseline disease severity and region. The estimated hazard ratios for each treatment group will be presented together with the corresponding 95% CI (based on Wald test).

Analysis will be illustrated using a Kaplan-Meier plot and the median time to hospital discharge will be estimated with 95% CIs for each treatment group. Subjects who die prior to Day 60 will be censored at Day 60 and trial withdrawals prior to Day 60 due to other causes than death without fulfilling the event will be censored at day of withdrawal. Subjects still in trial but not discharged from hospital at Day 60 will be censored at their Day 60 trial visit.

12.5.3.3 Oxygen Supplemental Free Days up to Day 29

Oxygen supplemental free days up to Day 29 will be defined as the number days for each subject with a score of ≤ 4 and no use of COVID-19 related supplemental oxygen. Refer to Section 10.13 for the derivation of number of oxygen free days.

Subjects who die prior to Day 29 will be given a value of -1 days in the analysis. Subjects who withdraw from the trial prior to Day 29 and have missing data will have their data multiply imputed as per Section 10.19.1. Subjects who chronically used supplemental oxygen prior to their COVID-19 illness will be considered oxygen free when they return to the same level of oxygen support they had been using prior to COVID-19.

Treatment groups will be compared using the Wilcoxon rank-sum test (using p-values) and the treatment difference will be expressed as the Hodges-Lehmann difference in median number of days with 95% CIs. All collected data post treatment will be used. Summary statistics for the number of oxygen free days will also be presented for each treatment group. A cumulative distribution plot of the number of oxygen free days by treatment arm will also be produced.

12.5.3.4 Subjects Free of Respiratory Failure at Day 15

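### SAP 10.14 ends the failure-free day count of discharged subjects at the Day 60 visit, not trial Day 60, so identical outcomes can score anywhere from 56 to 62 days

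*SAP*

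**What the plan says.** The endpoint is named as running up to Day 60 in the protocol objectives and in SAP 9.2.2. SAP 10.14 builds it as days in hospital with a score of 5 or less plus "the numbers of days a subject meets the criteria while discharged". Appendix 5 starts the count at Day 2 and refers back to 10.14 for the period between Day 29 and Day 60.

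The end of the count is worded differently by type of subject:

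- Inpatients with a score of 5 or less at both Day 29 and Day 60, and no recorded worsening: "the subject will be assumed to be respiratory failure free for all days between Day 29 and Day 60".
- Deaths: "If a subject dies, they will be considered in respiratory failure from the date of death up to Day 60".
- Discharged subjects with no change in status: if "they are not re-hospitalized due to a COVID-19 related illness, the number of respiratory failure free days after discharge will be calculated as" the Day 60 visit minus the date of discharge, plus 1.

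The schedules in both documents give the Day 60 visit a window of plus or minus 3 days. SAP 10.9 says that "the value collected at the Day 60 visit will be used in the analysis, even if this did not occur on trial Day 60". This carries the score across; it does not reset the date of the visit. SAP 12.5.4 specifies a Wilcoxon rank-sum test for the endpoint.

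**The concern.** The count for discharged subjects has no cap at trial Day 60. If the Day 60 visit means the date of the contact, the length of the counting period depends on when the site reached the subject. Survivors with the same course of illness then receive different scores, and some scores exceed the number of days the endpoint contains.

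A rank test is exposed to this. Discharged survivors who were never in failure after baseline should form one tied block. Spreading that block over several values puts timing noise where the test should see a tie, and lets a subject with real failure days outrank one with none.

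At stake are the reported day counts and the sensitivity of one non-key secondary endpoint. The testing hierarchy is not involved.

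**Working it through.** The documents state no figure for this point, so the check is direct enumeration followed by an illustration of the effect on the test.

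**Inputs.** Count starts on Day 2 (Appendix 5). Visit day V runs from 57 to 63 (both schedules). Post-discharge days are V - D + 1 for discharge on day D (10.14). Hospital and home days are added (10.14).

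**Day totals.** Take a subject with no score of 6 or more from Day 2 and no COVID-19 re-admission, with the discharge day counted once.

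- Hospital days, Day 2 to D - 1: D - 2.
- Home days: V - D + 1.
- Total: (D - 2) + (V - D + 1) = V - 1, whatever D is.

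For D = 8 the hospital part is 6. The home part is 50, 53 or 56 for visits on Day 57, 60 or 63, so the totals are 56, 59 and 62. Day 2 to Day 60 holds 60 - 1 = 59 days, so totals of 60, 61 and 62 cannot occur for the endpoint as named. With a fixed end at Day 60 every such subject scores 59.

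SAP 6.1 and 10.19.1 imply that the discharge day usually keeps its in-hospital score. The plus 1 then counts that day again and the totals become 57 to 63. The spread of 6 days is unchanged and ranks barely move.

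**Reversals.** A subject with k failure days seen on Day 63 scores 62 - k. This beats 56 for k = 1 to 5. With k = 3 the score is 59 against 56.

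**Frequency.** The documents do not give the distribution of visit days, so three are assumed: even over Day 57-63; half on Day 60 with the rest spread evenly; 80% on Day 60 with the rest spread evenly.

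- True ties broken, 1 minus the sum of squared day probabilities: 1 - 7 × (1/7)² = 0.857; 1 - (0.5² + 6 × (1/12)²) = 0.708; 1 - (0.8² + 6 × (1/30)²) = 0.353.
- Chance that a subject with k failure days outranks a never-failing one: k = 1, 0.306 / 0.243 / 0.119; k = 3, 0.122 / 0.042 / 0.007; k = 5, 0.020 / 0.007 / 0.001.

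**Power.** Tie-corrected Wilcoxon, 150 per arm, two-sided 5%, 8,000 replicates. All event rates are assumptions: geometric failure length, 25% of failures fatal, all survivors discharged.

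| Never in failure, placebo v C21 | Mean failure days, placebo v C21 | Fixed Day 60 | Even | Half | 80% |
|---|---|---|---|---|---|
| 80 v 90% | 9 v 9 | 0.678 | 0.259 | 0.289 | 0.406 |
| 80 v 88% | 12 v 6 | 0.511 | 0.242 | 0.256 | 0.322 |
| 60 v 70% | 15 v 8 | 0.575 | 0.471 | 0.476 | 0.516 |
| 45 v 62% | 15 v 15 | 0.790 | 0.643 | 0.679 | 0.733 |
| 45 v 55% | 15 v 8 | 0.638 | 0.611 | 0.609 | 0.617 |
| 20 v 30% | 15 v 9 | 0.795 | 0.773 | 0.781 | 0.787 |

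With no effect, rejection is 0.046 to 0.050. A second simulation (3,000 runs, visits even over the window) used the mortality assumed for sample size, 10% v 2.5%. Power fell from 65% to 37% at 75 v 85% never in failure, and from 86% to 63% at 65 v 80%.

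**Related point in SAP 10.15.** Subjects still in hospital at the end are counted to the date of trial completion, which gives 57 to 63 days. Withdrawals before discharge are set to 60. A subject never discharged but completing on Day 57 therefore scores better than a withdrawal.

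**The case against.** The strongest reply is that Day 60 visit can be read as nominal Day 60, in which case nothing is wrong beyond a loose phrase. The endpoint title says up to Day 60, and the sentence introducing the formula is itself limited to that period. The neighbouring rules in 10.14 treat Day 60 as one day, and imputed visits are given nominal days in 10.19.1. SAP 12.5.3.2 does use the visit as a date, since "Subjects still in trial but not discharged from hospital at Day 60 will be censored at their Day 60 trial visit", but 10.12 says the same subjects are censored at Day 60, so that comparison carries little weight.

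The nominal reading is possible but stated nowhere. The formula subtracts a date, 10.14 otherwise writes plain Day 60, and 10.9 distinguishes the visit from trial Day 60. Followed literally, the formula uses the visit date. The nominal treatment of imputed visits does not close the gap: a discharged subject with no Day 60 contact has no visit date to put in the formula, and scoring that subject at a nominal 59 beside observed subjects at 56 to 62 mixes two scales.

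Three other objections stand. Deaths are no evidence of unequal counting, because days after death add nothing wherever the period ends. The literal totals may be 57 to 63 instead of 56 to 62. The power figures depend on assumed rates, and the largest losses need 80 to 90% of subjects never in failure; subjects who enter with a score of 6 already meet the failure definition, and the split between scores 5 and 6 is not given.

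**Conclusion.** The concern holds. As written, the formula gives discharged survivors a counting period that moves with the visit: a 6-day spread among subjects who should share one value, and totals above the 59 days available. Those figures follow from the documents alone, given the visit-date reading.

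The effect on the test is noise. Its size ranges from negligible to severe, depending on visit timing and on the share never in failure; it is smaller when C21 also shortens failure. Type I error is not inflated if visit timing is unrelated to arm. The endpoint is a non-key secondary tested without multiplicity adjustment, so the primary and key secondary conclusions are untouched. It should be corrected, but it does not threaten the trial.

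**What to change.** In SAP 10.14 and Appendix 5:

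- Define the end of the count as trial Day 60, the date of first dose plus 59, for every subject, including those whose Day 60 score is imputed.
- Count each calendar day from Day 2 to Day 60 once. State whether the discharge day belongs to the hospital or the home count, and apply the same rule in the re-hospitalization formula.
- When the visit falls on Day 57 to 59, carry the last known status to Day 60; ignore days after Day 60.

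In SAP 10.15, end the count at trial Day 60 for subjects still hospitalized, so that a subject never discharged scores 60, the value already given to withdrawals before discharge.

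The cost is derivation wording and programming; no data collection changes.

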6.1 Changes from Protocol

- The protocol text uses "Major" and not "Important" to describe significant protocol violations. The SAP has been updated to use "Important" to align with CRO terminology. For the purposes of this trial major protocol deviations and important protocol deviations are interchangeable and have the same meaning as in the trial protocol.
- The protocol defines time to sustained discharge as "The first occurrence of a score ≤ 2 whereafter the score stays ≤ 2 for the remainder of the 60 days trial period", in the SAP this has been updated to state the time to date of discharge after which subjects are not re-hospitalized for COVID-19 reasons. These definitions are functionally equivalent. Due to how the ordinal scale is handled for other secondary endpoints (the day after discharge is the first value set to be ≤ 2) it is necessary to update the SAP definition to ensure that the initial day of discharge is used in the analysis for time to sustained discharge.
- Section 9.2 of the Protocol defines the Per Protocol population as: "All subjects in the ITT set without major protocol deviations deemed to have an impact on efficacy readouts. In addition, subjects who prematurely discontinued IMP during the treatment period but continued with data collection in the trial will also be excluded from the PP. Subjects withdrawn from the trial unrelated to trial participation due to extraordinary circumstances (for example subjects lost-to follow up due to unstable geopolitical situation) may also be excluded from the PP set (further specified in the SAP). Subjects will be included in the analyses according to the intervention they were randomized to.". For the SAP this will be update to exclude subjects with any important protocol deviations impacting efficacy or subjects who discontinue treatment due to subject decision or subjects not treated.

- Section 9.3.3 of the protocol states "Other endpoints assessing proportion of subjects will be compared using similar logistic regression models as for the primary endpoint with the treatment effect expressed as a difference in proportions." however the primary analysis of the primary endpoint does not use a logistic regression model, this SAP clarifies that this is the sensitivity analysis of the primary endpoint.

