10.15 Duration of Hospitalization

The duration of hospitalization will be calculated as

$$\text{Duration (days)} = \text{End date of hospitalization} - \text{Start date of hospitalization} + 1$$

The duration of multiple hospitalizations, including re-hospitalizations due to COVID-19 in the period will be summed together to derive the overall duration of hospitalization. For subjects who were hospitalized on the date of first dose of IMP, the date of first dose of IMP will be used as the start date. If a subject is still hospitalized at the end of the 60-day period the date of trial completion will be used.

For subjects who die they will be considered hospitalized from date of death through Day 60. For subjects who discontinue the trial prior to discharge from hospital, the number of days of hospitalization will be set to 60 days (it will be assume they did not discharge from hospital). If a subject discontinues the trial following discharge for reasons other than death and there is no further hospitalization data available then for the purpose of the analysis the subject will be considered to be not re-admitted in the period and no additional imputed days will be added to the number of days recorded on the available assessments.

An additional sensitivity analysis will be performed where missing data will be imputed as per Section 10.19.1, such that subjects who are early withdrawals will have data imputed following withdrawal and

where all re-hospitalizations are considered as COVID-19 related regardless of the investigator indicated cause.

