A subject will be considered free of respiratory failure at a time point if the value of the 8-point ordinal scale is ≤ 5 . For details on this derivation refer to Section 10.13. For each of the datasets imputed in step 2, the analysis as per Section 12.5.3.3 will be implemented.

Other Non-Key Secondary Endpoints

For the endpoints of proportion of subjects on invasive mechanical ventilation or ECMO at Days 8, 15, 22, 29 and 60, a subject will be considered on invasive mechanical ventilation or ECMO if the imputed value at the time point is ≥ 7 .

For the endpoint of proportion of subjects on non-invasive, invasive mechanical ventilation, ECMO or supplemental oxygen use at Days 8, 15, 22, 29 and 60, subjects will be considered on non-invasive, invasive mechanical ventilation, ECMO or supplemental use if they have an imputed or observed score of ≥ 5 at the time point.

For sensitivity analysis for the endpoint of duration of hospitalization, the duration of multiple hospitalizations, including re-hospitalizations due to COVID-19 and non-COVID-19 related reasons in the period will be summed together to derive the overall duration of hospitalization. For subjects with no missing data, duration of hospitalization will be calculated as per Section 10.15. For subjects with missing data following observed discharge date, no additional days will be added for

duration if the imputed values are ≤ 2 following this date, otherwise if subjects have a value of > 2 following last observed discharge, the number of days where the imputed values are > 2 will be added to the observed duration. For subjects with missing data with no observed discharge date, if the imputed values are ≤ 2 , then the subject will have the duration of hospitalization calculated as relative day of last value > 2 – start date of hospitalization +1. If the subject has multiple values > 2 following the first imputed discharge, the number of days where the imputed value is > 2 will be added to the duration. Note that Day 59 should be used in the calculation if imputed Day 29 is > 2 and imputed Day 60 ≤ 2 . If imputed Day 29 ≤ 2 and Day 60 > 2 only Day 60 will be counted as in hospital.. If a subject does not have the event across the imputed and observed data duration will be calculated as Day 60/study completion – date of initial hospitalization +1.

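### Three day-count rules for non-key secondary or sensitivity endpoints (SAP 10.14 and 10.19.1) give wrong or conflicting values as written

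*SAP*

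**What the plan says.** **Respiratory failure free days (SAP 10.14).** The endpoint is the number of post-baseline days with an ordinal score of 5 or less. For a discharged subject who is not re-admitted for COVID-19, "the number of respiratory failure free days after discharge will be calculated as" the Day 60 visit date minus the discharge date, plus one. For a subject re-admitted with a score of 6 or more, the interval between stays is the re-admission date minus the discharge date. The total adds days with a score of 5 or less "on the 8-point ordinal scale while hospitalized and the numbers of days a subject meets the criteria while discharged".

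**The discharge day.** SAP 10.19.1 says that if a scheduled score other than 2 exists, "this value will be used in the analysis for the day of discharge". If the score is missing or 2, the day becomes 1 or 2 on the adjusted scale. SAP 6.1 describes the general handling: "the day after discharge is the first value set to be" 2 or lower.

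**Appendix 5** defines the same endpoint as a sum of daily scores from Day 2 to Day 29 plus Day 60. It sends only the days between Day 29 and Day 60 to 10.14.

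**Days 29 to 60 (SAP 10.14, first bullet).** If both readings are 6 or more, "the subject will be assumed to be in respiratory failure for all days between Day 29 and Day 60". The other three bullets use observed changes or known dates of change.

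**Duration of hospitalization.** In SAP 10.15, for subjects in hospital at first dose, "the date of first dose of IMP will be used as the start date". Deaths count as hospitalized through Day 60. The imputed sensitivity version in 10.19.1 reads: "If a subject does not have the event across the imputed and observed data duration will be calculated as Day 60/study completion" minus the date of the initial admission, plus one. Its other formula, and Appendix 5, subtract the hospitalization start date.

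**The concern.** Both endpoints are compared between arms with Wilcoxon rank-sum tests (SAP 12.5.4), so what matters is whether the assigned values rank subjects correctly.

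- If the discharge day sits in both parts of the 10.14 sum, every discharge adds a day that does not exist. A re-admitted subject gains two and can tie with a subject who never failed.
- The first bullet can turn documented failure-free days into failure days. Protocol 8.2.1 requires a new score at each status change for subjects hospitalized between Day 29 and Day 60, so the data to avoid this are collected.
- If an imputed duration runs from admission while a death runs from first dose, a survivor can rank worse than a death. SAP 10.19 gives deaths the worst value in every efficacy analysis.

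**Working it through.** **The plan's own figure.** SAP 10.15 assigns 60 days to a subject who leaves the trial before discharge. From first dose (Day 1) to Day 60: 60 − 1 + 1 = 60. This reproduces.

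**1. Discharge day.** Take a subject with a score of 5 or less on every day, discharged on Day *d*, with the Day 60 visit on Day 60.

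- In-hospital days 2 to *d*, discharge day included: *d* − 1.
- After discharge: 60 − *d* + 1.
- Sum: 60 for any *d*. Only 60 − 1 = 59 distinct days exist from Day 2 to Day 60.
- The same subject never discharged gets 59.

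Re-admission example: discharged Day 10, re-admitted Day 20 with score 6, score 5 or less on Days 21 and 22, discharged Day 22.

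| Part | Days |
|---|---|
| First stay, Days 2–10 | 9 |
| Between stays, 20 − 10 | 10 |
| Second stay, Days 21–22 | 2 |
| After second discharge, 60 − 22 + 1 | 39 |
| Total as written | 60 |
| True value, 59 less Day 20 | 58 |

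The end point also moves. The formula uses the Day 60 visit, which may fall 3 days either side. For the never-failing subject the total equals the trial day of that visit: 57, 60 or 63, against 56, 59 or 62 distinct days.

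**2. First bullet.** With scores of 6 or more on both Day 29 and Day 60, recorded scores of 5 or less on Days 35 to 50 are lost: 50 − 35 + 1 = 16 days. The maximum is Days 30 to 59: 59 − 30 + 1 = 30 days. By contrast, under the third bullet, a known improvement on Day 35 that holds to Day 60 earns 60 − 35 + 1 = 26 days.

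**3. Imputed hospital duration.** Let *k* be days in hospital before first dose. SAP 12.2 tabulates 0 to 5. This agrees with exclusion criterion 6 (at most 72 hours in hospital at screening) plus a screening period of up to 48 hours: 3 + 2 = 5.

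- No discharge imputed: 60 + *k*, that is 60, 61, 62, 63, 64 or 65.
- Death in hospital, counted from first dose through Day 60: 60.
- Discharge imputed only at Day 60 (last in-hospital day 59), if the start is read as admission: 59 + *k*, which exceeds 60 once *k* is 3 − 1 = 2 or more (59 + 2 = 61).
- Started at first dose instead: 60 and 59 respectively, so no imputed survivor exceeds a death.

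**The case against.** The best defence of 10.14 is that its two post-discharge formulas agree with each other if the discharge day belongs to the discharged part. Hospital days then stop at *d* − 1, and a single discharge gives (*d* − 2) + (61 − *d*) = 59. The re-admission example gives 8 + 10 + 1 + 39 = 58. Both are correct. That reading is natural where the discharge-day score is missing or 2. It does not stand as the general rule, because 6.1 and 10.19.1 keep a scheduled in-hospital score for that day and "The number of respiratory failure free days will be the sum of the days the subjects met the criteria" without removing an overlap. A reader might infer that the formulas are wrong on any reading. The documents do not go that far: the result depends on which part owns the day, and Appendix 5 counts daily scores once.

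Other points stand in part. Subjects discharged once mostly gain the same day, so their ranks among themselves do not change. Under the first bullet, a subject discharged after Day 29 and re-admitted for COVID-19 with a score of 6 or more is partly covered by the re-admission formula, and the 30-day loss is an extreme.

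For duration, a reader might infer that everyone except the imputed never-discharged subject is counted from first dose. That is not literal. The other imputed formula and Appendix 5 use the hospitalization start date, which can be read with the 10.15 convention (giving 60 when no discharge is imputed) or as admission. The initial-admission wording in 10.19.1 for the no-discharge case is explicit, so the conflict remains.

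**Conclusion.** The point holds as a minor correction to stated rules.

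1. Where the discharge day keeps its in-hospital score of 5 or less, 10.14 counts it twice: one extra day per discharge, so 60 in a 59-day window with a Day 60 visit on Day 60. This conflicts with Appendix 5.
2. The first bullet ignores recorded improvement, mainly for subjects who improve without discharge and are failing again at Day 60. Such subjects should be rare.
3. In one sensitivity analysis, an imputed never-discharged subject gets 60 to 65 days against 60 for an in-hospital death, contrary to 10.15 and 10.19. This assumes 0 to 5 days in hospital before first dose, as in the SAP's own categories, and an end at Day 60.

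It would be a mistake to infer that the trial's main conclusions are at risk. Both endpoints are outside the testing hierarchy, and no primary or key secondary result uses these rules. The documents do not give the number of affected subjects, so the effect on the Wilcoxon tests cannot be sized.

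**What to change.** - **SAP 10.14 and Appendix 5:** state that each trial day from Day 2 to Day 60 is counted exactly once, with the discharge day classified by its analysis score. End the count at trial Day 60 and not at the Day 60 visit, and use one derivation in both places. Simply subtracting a day from the formula is not safe: where the discharge day is not counted in hospital, a never-failing subject would get (*d* − 2) + (60 − *d*) = 58.
- **SAP 10.14, first bullet:** add that the rule applies unless recorded scores or dates show otherwise.
- **SAP 10.19.1 and Appendix 5, imputed hospitalization duration:** start every formula at the date of first dose, as in 10.15, and cap the end at Day 60. The trial-completion end date in 10.15 deserves the same cap, since a subject still in hospital at a Day 63 visit gets 63 days.
- **While editing:** 10.19.1 refers to 10.13 for the respiratory failure derivation, and it should refer to 10.14.

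The cost is a few wording changes and matching code. No new data are needed.
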